Study Protocol (Version 3; dated 7/2/2012)

1. Title of project

Omega-3 fatty acids and inflammation in normal weight and obese subjects

Short title: Omega-3 fatty acids and inflammation

2. Chief investigator

[name], Institute of Human Nutrition, Faculty of Medicine, University of Southampton

3. Funder of project

European Commission

4. Duration of research

36 months from start date

5. Places where research will be conducted

University of Southampton and Wellcome Trust Clinical Research Facility, Southampton University Hospitals NHS Trust

6. Researchers involved

[name], [name], [name], [name], [name]

7. Purpose of project/Background

Seafood, especially oily fish, and fish oil capsules contain relatively high amounts of two long chain omega-3 (n-3) fatty acids called eicosapentaenoic acid (EPA; 20:5n-3) and docosahexaenoic acid (DHA; 22:6n-3). These fatty acids are known to be important for human health [1,2] and the UK Government recommends that their intake be increased [3]. Amongst the physiological effects of n-3 fatty acids is an anti-inflammatory action [4]. Obesity is now recognised as a state associated with chronic low-grade inflammation [5]. In response to a meal there is a transient increase in inflammation, manifested as increased concentrations of inflammatory mediators in the bloodstream [6]; this is referred to a post-prandial inflammation. This response is exaggerated by a high fat content of the meal and in obese subjects and type 2 diabetics [7,8]. Inflammation is considered to increase cardiovascular risk [9]. Thus, the increased inflammatory state in obesity and following consumption of a meal are believed to increase cardiovascular risk [10]. Most demonstrations of the anti-inflammatory effect of n-3 fatty acids have been in healthy individuals or in the context of cardiovascular disease or a frank inflammatory condition like rheumatoid arthritis. It is not clear whether n-3 fatty acids exert anti-inflammatory effects in obese subjects or in the post-prandial state. This research will investigate these two areas. This research is important to regulators, health professionals and the health service, consumers and specific patient groups (e.g. those with obesity). We plan to investigate the anti-inflammatory action of n-3 fatty acids in normal weight and obese subjects.

8. Objectives

The overall objective is to identify whether n-3 fatty acids are anti-inflammatory in both normal weight and obese subjects.

The specific objectives are:

1. To follow the appearance of inflammatory mediators in the bloodstream of normal weight and obese subjects over 6 hours following consumption of a standard high fat meal and of the same meal consumed in conjunction with capsules providing EPA+DHA.

- 2. To identify the concentrations of inflammatory mediators in the bloodstream of normal weight and obese subjects before and after 12 weeks of consumption of capsules providing EPA+DHA or placebo.
- 3. To identify the presence of inflammatory cells and expression of inflammatory genes and proteins in adipose tissue of normal weight and obese subjects before and after 12 weeks of consumption of capsules providing EPA+DHA or placebo.
- 4. To follow the appearance of inflammatory mediators in the bloodstream of normal weight and obese subjects who have been consuming n-3 fatty acids or placebo for 12 weeks over 6 hours following consumption of a standard high fat meal.

The questions being addressed by this study are:

- 1. Is the post-prandial inflammatory response different in obesity?
- 2. Can consuming marine n-3 fatty acids with a meal alter the post-prandial inflammatory response to that meal?
- 3. Is the chronic effect of marine n-3 fatty acids on inflammation different between normal weight and obese subjects?
- 4. Can marine n-3 fatty acids reduce inflammation within adipose tissue?
- 5. Does chronic use of marine n-3 fatty acids alter the post-prandial inflammatory response?

9. The study

General approach to be taken

We will recruit normal weight and obese subjects. For the purpose of this study obesity will be defined as a body mass index (BMI) > 30 kg/m^2 and a waist circumference $\geq 94 \text{ cm}$ for men and $\geq 80 \text{ cm}$ for women. Subjects' post-prandial inflammatory response to a high fat meal and to n-3 fatty acids taken with that meal will be assessed using approaches we have used previously to study acute lipid metabolism and fatty acid appearance in the bloodstream [8,9]. Blood will be taken at several time points during the meal challenge (0, 1, 2, 3, 4 and 6 hours). Each subject will undergo both meal challenges, in random order and separated by at least 2 weeks. Subjects will then be randomised to consume placebo or "fish oil" capsules daily for about 12 weeks. Inflammatory mediators in the bloodstream will be measured at the start and end of this period. Subjects will then repeat the standard meal challenge. A range of inflammatory mediators will be measured in the blood samples. In addition, fatty acid status will be measured in all samples. An adipose tissue biopsy will be taken at study entry and after the 12 week intervention period; this will be used to assess inflammatory cell infiltrate and the levels of genes and proteins involved in inflammation.

Subjects and supplements

Subjects aged 18 to 65 years with normal weight (a body mass index (BMI) between 18.5 and 25 kg/m² (n = 50)) and obesity (BMI 30 to 40 kg/m^2 (n = 50) and a waist circumference $\geq 94 \text{ cm}$ for men and $\geq 80 \text{ cm}$ for women) will be recruited. Subjects will recruited via posters and email shots in the University of Southampton, Southampton General Hospital, and other organisations with which the researchers have contact; and via advertisements in local media including newspapers and radio. Subjects who express an interest will be screened by telephone interview. If they fit the inclusion and exclusion criteria (see below) they will be sent the information sheet. They will be contacted about 7 days later to confirm their interest or not, and if they remain interested an appointment will be made for them to visit the Wellcome Trust Clinical Research Facility at Southampton General Hospital. At this first visit the study will be explained, any questions answered and written consent obtained. Subjects will later make three clinic visits.

The n-3 fatty acid preparation to be used is commercially available as a supplement and will be provided in capsules. Approximately 1.8 g EPA plus DHA will be given during the meal challenge and then will be given per day during the chronic phase of the study. This dose of n-3 fatty acids is similar to that used in many previous studies and is an amount consistent with the Government's

guideline range for oily fish consumption [3]. The placebo capsules will be identical in size and appearance to the fish oil capsules and will contain vegetable oil. Subjects, researchers and clinical staff will be blinded to group allocation.

Inclusion criteria

- 1. Male or female
- 2. Aged 18 to 65 years
- 3. Body mass index 18.5 to 25 or 30 to 40 kg/m^2
- 4. If body mass index is 30 to 40 kg/m² waist circumference is ≥ 94 cm for men or ≥ 80 cm for women
- 5. Not consuming fish oil or other oil supplements
- 6. Not eating more than one oily fish meal per week
- 7. Willing to adhere to the study protocol
- 8. Being able to provide written informed consent

[figure not shown]
Exclusion criteria

- 1. Aged < 18 or > 65 years
- 2. Body mass index $< 18.5, 25-29.9 \text{ or } > 40 \text{ kg/m}^2$
- 3. If body mass index is 30 to 40 kg/m^2 waist circumference is < 94 cm for men or < 80 cm for women
- 4. Diagnosed diabetes
- 5. Use of prescribed medicine to control inflammation
- 6. Use of prescribed medication to control blood lipids (e.g. statins, fibrates (fenofibrate), Omacor)
- 7. Use of prescribed medication to control blood pressure (ACE inhibitors, angiotensin 2 receptor blockers, calcium channel blockers, α-inhibitors, thiozide diuretics)
- 8. Use of fish oil or other oil supplements
- 9. Chronic gastrointestinal problems (e.g. IBD, celiac disease, cancer)
- 10. Pregnant or planning to become pregnant within the study period
- 11. Participation in another clinical trial

Subject participation schedule

Subjects who express an interest will be screened by telephone interview. If they fit the inclusion and exclusion criteria they will be sent the information sheet. They will be contacted about 7 days later to confirm their interest or not and if they remain interested an appointment will be made for them to visit the Wellcome Trust Clinical Research Facility, Southampton General Hospital. At this first visit the study will be explained, any questions answered and written consent obtained; subjects will then have height, weight, waist and hip circumference, and body composition (bioelectrical impedance) measured to confirm that they meet the inclusion criteria. A 9 ml blood sample will be taken for preparation of DNA. An appointment will be made for the first clinic visit; subsequently two further clinic visits will be made (i.e. three clinic visits in total after the initial "consenting" visit). Subjects will attend each of these three clinic visits in the fasted state (no food or drink except water after 9 pm the previous evening).

Subjects will visit the Wellcome Trust Clinical Research Facility, Southampton General Hospital on three occasions each between 8 and 10 am. On each occasion they will be in the fasted state. At each clinic visit weight, waist and hip circumference, and body composition (bioelectrical impedance) will be measured. Two visits will be for post-prandial study days prior to entering the chronic phase of the study. The third visit will be at the end of the chronic phase of the study, at which time a further post-prandial study day will occur. An adipose tissue biopsy will be taken from the subcutaneous abdominal area at the first and third clinic visits.

During the post-prandial study days subjects will have a venous cannula inserted and 20 ml blood will be collected at zero time. They will then consume a standard breakfast (on one occasion with placebo capsules and on the other with fish oil capsules – this will be in random order; on the third post-prandial day only the placebo capsules will be used) and 5 ml blood will be collected at each later time point (1, 2, 3, 4 and 6 hours). Thus 45 ml blood will be collected per visit. Blood will be taken into heparin. An small adipose tissue biopsy (weighing 1 to 5 g) will be taken from the subcutaneous abdominal area at the end of the first and third clinic visits; this will be taken under local anaesthetic. At the end of each visit subjects will be offered toast and a hot drink. Subjects will receive a supply of supplements along with instructions on how to take them at the second clinic visit.

As indicated above a small adipose tissue biopsy will be taken at two of the clinic visits. The wound will be stitched and subjects will return to the Wellcome Trust Clinical Research Facility about one week later in order for the stitches to be removed.

Schedule of subject visits and activities performed at each visit

X indicates the activity will take place.

Visits 3 and 4 will be about 12 weeks apart and subjects will consume fish oil or placebo capsules daily during that period.

Activity	Visit 1	Visit 2	Visit 3	Visit 4
		(Clinic visit 1)	(Clinic visit 2)	(Clinic visit 3)
Subject in fasting state		X	X	X
Informed consent	X			
Height	X			
Weight	X	X	X	X
Waist & hip circumference	X	X	X	X
Bioelectric impedence	X	X	X	X
Blood for DNA	X			
Post-prandial study: Blood for		X	X	X
fatty acids & inflammatory				
markers				
Adipose tissue biopsy		X		X

Sample analysis

Blood collected at study entry will be used to prepare DNA which will be stored and used later to seek to identify genetic factors (for example polymorphisms in genes related to lipid metabolism or inflammation) that might explain differences among individuals seen in the study. Adipose tissue biopsy material will be stored frozen at minus 80°C. Blood will be used to prepare plasma, mononuclear cells and red cells. Plasma will be aliquoted and frozen at minus 80°C. Mononuclear cells and red cells will be frozen at minus 80°C. Lipid will be extracted from plasma and red cells using chloroform/methanol and fatty acid composition determined using standard techniques. Inflammatory proteins in plasma will be measured by flow cytometry and ELISA. Lipid mediators of inflammation will be measured by mass spectrometry. Inflammatory proteins on the surface of mononuclear cells will be determined by flow cytometry. Inflammatory genes and proteins within mononuclear cells and adipose tissue will be determined by immunohistochemistry.

Data will be compared across time and between groups by ANOVA with repeated measures.

10. Data handling and record keeping

- All data will be entered onto a spreadsheet (Microsoft Excel) by the researchers involved.
- All data will be entered on a password-protected computer. This data will be accessed only by the PI and the researchers involved.
- All data will only be linked to study codes and thus not identifiable with the source volunteer. However, the caveat to this will be a data set recording the volunteer name and study code without any other volunteer details.
- All data recorded on paper will be kept in a locked filing cabinet in the researchers' office and/or in a dedicated, restricted access, clinical data storage area on Level D of the IDS Building, University of Southampton.
- Data of an identifiable nature (i.e. volunteer names, contact details, addresses) will be destroyed 12 months after the end of the study. All other data will be kept securely for 15 years and then destroyed.
- Data will be obtained, handled and stored in adherence to the principle set out in the Data Protection Act 1998.
- The investigators will permit monitoring, audits, REC and MHRA review (as applicable) and provide direct access to source data and documents.

11. Statistical Analysis

The statistical analysis will involve the comparison of inflammatory markers (proteins, lipids etc) and of fatty acids between normal weight and obese subjects and between placebo and n-3 fatty acid treatments. All statistical comparisons will be performed at the end of the study using SPSS version 14.

12. Sample size calculation

Sample size is calculated based upon the chronic intervention phase of the study. We have considered the typical means and standard deviations of prototypical inflammatory mediators (such as interleukin-6) that we have measured previously and an anticipated 20% reduction in these concentrations by n-3 fatty acids. A sample size of 20 subjects per treatment group (i.e. placebo; n-3 fatty acid) will be required to detect a 20% difference in inflammatory markers with 80% power at the 5% significance level (p < 0.05). This number is also consistent with the number of subjects studied by others in investigations of post-prandial inflammation [7,8]. Thus, 40 normal weight and 40 obese subjects will be required to be recruited to satisfy the sample size calculation for the chronic phase of the study. To allow for a 20% drop out rate, 50 normal weight and 50 obese subjects will be recruited.

13. Safety assessments

The n-3 fatty acid supplement to be used is commercially available and is safe. Two invasive procedures will be used, adipose tissue biopsy and obtaining blood samples. The biopsy will be taken by a trained surgeon with assistance from trained nursing staff and blood samples will be taken by trained nursing staff limiting the likelihood of adverse events related to participation in the study. However if any volunteer reports any untoward medical occurrence this will be recorded on an adverse event or serious adverse event form and the PI informed immediately. If the investigator suspects that a serious adverse event is either a) related to the intervention or b) unexpected, the PI will report the event to the main REC and to a representative of the supplier of the supplement. An adverse or serious adverse event may result in the volunteer wishing to withdraw from the study or being unable to continue with the study schedule. In this case or any other instance in which a subject withdraws or is withdrawn from the study a volunteer withdrawal form will be completed. Where the reason is know to the investigator or is volunteered by the subject this will be recorded on the form. The subject will not be required to give any reason for withdrawing themselves from the study and will not be asked to do so by the investigator.

14. Stopping/Discontinuation of intervention

Completion of each subject's involvement in the study will be when the last blood sample is taken, which will be approx. 15 weeks after the subject entered the study. If there is any reason for discontinuing the intervention prior to its completion the PI will arrange for the research team to inform all volunteers immediately. The PI will also inform the sponsor and the main REC.

15. Monitoring

The project will be overseen and monitored by the Southampton University Hospitals Trust R&D Office.

Steps taken to ensure quality of research

Standard operating procedures will be developed for all aspects of the study. Staff will be fully trained in all procedures in which they are involved. All activities will conform to local health and safety regulations and staff will be adequately trained in these. Good clinical practice and good laboratory practice will be used throughout the study. Staff involved in blood sampling will be properly trained for this. All study samples will be labelled clearly, uniquely, accurately and durably using distinctive water resistant labels printed via computer. All samples will be tracked. The

temperatures of fridges and freezers in which samples are stored will be monitored to ensure proper functioning. All analyses will be conducted to the highest standards. All equipment to be used is modern, in good working order and maintained on service contracts. All pipettes to be used are serviced regularly. All data will be recorded in laboratory notebooks that will be signed off by the PI at regular intervals. Data entry into spreadsheets will be carefully monitored. All data will be stored securely.

16. Ethical considerations

The study will involve the participants consuming a supplement over the course of several weeks and providing a series of blood samples. Participants will not be aware of whether they are consuming the placebo or n-3 fatty acid supplement. Participants will be given an information sheet outlining the nature of the study and they will have the opportunity to discuss any issues they may have with the research staff. Participants will most likely be familiar with having blood sampled, but they will not be familiar with adipose tissue biopsy. This will be explained fully and subjects will be provided with a specific information sheet related to this procedure. Trained researchers will address any concerns that the participants may have. If they remain concerned they will be reminded that they can opt out of any procedure at any time.

- **17.** This study will be conducted in accordance with approvals from the LREC and the Southampton University Hospitals Trust R&D Office.
- **18.** This study will be conducted in compliance with the Research Governance Framework for Health and Social Care, the Medicine for Human Use (Clinical Trials) Regulation 2004 and ICH GCP.

19. Financial arrangements

This study is funded by the European Commission.

20. Indemnity

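### Exclusion 5 stops at prescribed anti-inflammatory medicine, and no clinic visit asks about recent anti-inflammatory use or infection, so avoidable noise can enter the inflammatory outcomes

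*Protocol*

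**What the plan says.** All references are to the protocol.

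- **Section 9, exclusion criteria.** Exclusion 5 is "Use of prescribed medicine to control inflammation". Exclusion 6 is likewise limited to prescription: "Use of prescribed medication to control blood lipids (e.g. statins, fibrates (fenofibrate), Omacor"). Exclusion 7 does the same for blood pressure medication. Exclusion 8, on oil supplements, has no such limit and so reaches products a subject buys without a prescription.
- **Chronic disease.** The disease exclusions are "Diagnosed diabetes" (exclusion 4) and "Chronic gastrointestinal problems (e.g. IBD, celiac disease, cancer") (exclusion 9).
- **Section 9, subject participation schedule.** "Subjects will attend each of these three clinic visits in the fasted state", with arrival between 8 and 10 am. The visit table lists fasting, body measurements, blood sampling and biopsy. It has no row for medication use, current illness or infection, and no rule for postponing a visit is given.
- **Section 8.** The outcomes are inflammatory mediators. Objective 2, for example, is: "To identify the concentrations of inflammatory mediators in the bloodstream of normal weight and obese subjects before and after 12 weeks of consumption" of the capsules.
- **Section 12.** The sample size rests on "an anticipated 20% reduction in these concentrations by n-3 fatty acids", with 20 subjects per treatment group within each weight group.

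**The concern.** The only evident purpose of exclusion 5 is to keep medicine that alters inflammation out of a study that measures inflammation. That purpose does not depend on whether the medicine was prescribed. Exclusion 8 shows that the same list can reach self-bought products where this is intended. As written, a regular user of a non-prescribed anti-inflammatory passes every criterion.

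The visit procedures do not make up for this. Nothing asks a subject on the day whether such a medicine was taken recently or whether an infection is present. An analyst who later sees an extreme value has no systematic record with which to explain it, set it aside in a sensitivity analysis or adjust for it. A statistical analysis plan cannot use information that the visits never collect.

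Two comparisons are exposed in different ways. Placebo versus n-3 is randomised, so affected subjects fall into either arm by chance, and the cost is wider spread and lower power. Normal weight versus obese (study question 1) is an observational contrast. If non-prescribed use or illness differed between the weight groups, the estimate would be biased, and a larger sample would not cure that.

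**Working it through.** **1. Reading of the criteria.** All 8 inclusion and 11 exclusion criteria were checked against two situations.

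| Situation | Covered by a criterion or visit rule? |
|---|---|
| Regular non-prescribed anti-inflammatory use | No; exclusion 5 is limited to prescribed medicine |
| Recent anti-inflammatory use or acute infection at a clinic visit | No; only fasting and time of day are set |

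**2. The plan's own figure.** Section 12 gives 20 per group for a 20% difference at 80% power and 5% significance, but no standard deviation (SD), so the 20 cannot be reproduced directly. Solving for the coefficient of variation (CV), with a two-sided test assumed:

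CV = 0.20 / [√(2/20) × (1.960 + 0.842)] = 0.20 / (0.3162 × 2.802) = 0.226.

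The design therefore implies a CV of about 22.6% (22.0% with the t distribution). The dropout step reproduces: 40 / (1 − 0.20) = 50.

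**3. One affected value in an arm of 20.** The fold-changes k are assumptions; the documents give none.

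- Shift in arithmetic mean = (k − 1)/20
- Shift in geometric mean = k^(1/20) − 1

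| k | Arithmetic mean | Geometric mean |
|---|---|---|
| 3 | +10% | +5.6% |
| 5 | +20% | +8.4% |
| 10 | +45% | +12.2% |

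**4. Would that create a false effect?** Take two idealised normal arms of 20 at CV 22.6%, multiply one central value in one arm by k, and apply an equal-variance t-test. For k = 5 the SD of that arm rises from 0.226 to about 0.94. The standard error of the difference is √[(0.226² + 0.94²)/20] ≈ 0.216 against a shift of about 0.20, so t ≈ 0.94 and p = 0.35. For k = 3, 5 and 10, p = 0.42, 0.35 and 0.33 (log scale 0.56, 0.48 and 0.41). Three such values, all in the same arm, still give p of 0.08 to 0.10 on the raw scale.

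**5. Loss of power.** Suppose a share f of subjects in both arms has the marker multiplied by m on the day (both assumed), and the treatment effect stays at 20% of the mean.

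- Mean = 1 + f(m − 1)
- Variance = (1 − f)CV² + f(m·CV)² + f(1 − f)(m − 1)²
- Power = Φ[0.20 / (CV′ × √(2/20)) − 1.960], where CV′ = √variance / mean

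For f = 5%, m = 2: mean 1.05; variance 0.0484 + 0.0102 + 0.0475 = 0.106; CV′ = 0.326/1.05 = 0.310; power = Φ(2.04 − 1.96) = 53%.

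| f | m | CV′ | Power at 20 per group | n per group for 80% |
|---|---|---|---|---|
| 0 | – | 0.226 | 80% | 20 |
| 5% | 1.5 | 0.251 | 71% | 25 |
| 5% | 2 | 0.310 | 53% | 38 |
| 10% | 1.5 | 0.269 | 65% | 29 |
| 10% | 2 | 0.359 | 42% | 51 |

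**The case against.** Several stronger readings are tempting, and the documents do not support them.

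- **That these two exclusions (5 and 9) are the only protection, or that every such subject will enter.** Diabetes, prescribed lipid and blood pressure medication and oil supplements are barred as well. Affected subjects can enter; how many would do so is unknown.
- **That the background itself calls for barring all inflammatory disease.** Section 7 says most evidence comes from healthy individuals or "in the context of cardiovascular disease or a frank inflammatory condition like rheumatoid arthritis". Healthy individuals stand in the same list and are also enrolled here, so the sentence implies no exclusion. Barring every chronic inflammatory disease would also narrow the obese population that the objectives describe. That is a trade-off, not a correction.
- **That the first biopsy drives self-medication into the second meal challenge.** The biopsy is taken at the end of clinic visit 1, stitches come out about a week later, and the challenges are at least 2 weeks apart. Self-treatment would have to continue for about a week after stitch removal.
- **That ill subjects must be sampled.** The protocol is silent; it does not require this. The visit spacing already leaves room to rebook. Section 13 records untoward medical events that a volunteer reports, and section 15 promises standard operating procedures for all aspects of the study.
- **That one extreme value can create the anticipated effect.** It can move a mean by that much, but the inflated SD keeps the test far from significance.

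These limits stand and make the point a small one. They do not remove it. Adverse event forms depend on volunteered reports and would not capture routine non-prescribed use, and the protocol does not say that the operating procedures cover visit-day checks. It is also fair that unequal use between the weight groups is a possibility, not something the documents show.

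**Conclusion.** The point holds as a cheap improvement of minor severity. Exclusion 5 is narrower than its purpose, and the clinic visits neither check nor record recent anti-inflammatory use or infection.

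For placebo versus n-3 the consequence is lost power, not bias. For normal weight versus obese it is possible bias in study question 1, of unknown direction and size.

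No size can be taken from the documents. Under the assumed shares and multipliers above, power falls from 80% to between 71% and 42%. Those figures rest on the implied CV of 22.6%, on 5% or 10% of subjects being affected, and on markers raised 1.5- or 2-fold. They illustrate sensitivity and do not predict the loss.

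**What to change.** 1. Reword exclusion 5 to cover regular use of prescribed or non-prescribed anti-inflammatory medicine.
2. At each clinic visit, ask about recent anti-inflammatory use and current or recent infection, and record the answers. Add a row for this to the visit table.
3. Rebook the sampling visit when either is reported within a window that the investigators fix in advance. The existing allowances, a minimum of 2 weeks between meal challenges and about 12 weeks of supplementation, leave room for this.

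The change governs eligibility and when samples are taken. It does not restrict what a subject may take. A blanket exclusion of chronic inflammatory disease is not recommended.

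The cost is protocol wording, one extra question per visit, a slightly smaller recruitment pool and occasional delayed visits.

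### The baseline adipose biopsy follows a meal with randomly ordered fish oil or placebo capsules, the 12-week biopsy always placebo capsules, so within-arm before/after changes are not like for like

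*Protocol*

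**What the plan says.** Section 8 makes adipose tissue the subject of objective 3 (inflammatory cells, genes and proteins before and after 12 weeks of EPA+DHA or placebo) and of question 4 (whether n-3 fatty acids reduce inflammation within adipose tissue).

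Section 9, General approach, describes the sampling in outline: "An adipose tissue biopsy will be taken at study entry and after the 12 week intervention period". The Subject participation schedule adds the hour: the biopsies are "taken from the subcutaneous abdominal area at the end of the first and third clinic visits". Both are post-prandial study days with blood drawn up to 6 hours after breakfast.

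At clinic visits 1 and 2 the breakfast is eaten "on one occasion with placebo capsules and on the other with fish oil capsules". On order, the General approach says: "Each subject will undergo both meal challenges, in random order and separated by at least 2 weeks". On amount, Subjects and supplements says: "Approximately 1.8 g EPA plus DHA will be given during the meal challenge", the same amount as the daily dose in the chronic phase. For clinic visit 3, "on the third post-prandial day only the placebo capsules will be used".

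The 12-week allocation is a separate step after the two challenges: "Subjects will then be randomised to consume placebo or" fish oil capsules daily. Sample analysis names repeated-measures ANOVA across time and between groups. Section 11 compares placebo with n-3 treatment and normal weight with obese subjects.

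**The concern.** A before-treatment sample should be free of the treatment under study. Here some first biopsies are taken about 6 hours after an n-3 dose equal to a full day of the chronic supplement, and some after placebo capsules. No follow-up biopsy is preceded by fish oil at that day's meal. Both biopsies follow the same standard meal, so the mismatch lies in the capsule and not in the meal.

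The protocol cannot assume this away. Question 2 in section 8 asks whether n-3 fatty acids taken with a meal alter the inflammatory response to it, and objective 1 follows that response over the same 6 hours. The blood baseline is not affected, because it is a fasting zero-time sample; only the adipose baseline is exposed.

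At stake is any statement that adipose inflammation fell, or did not fall, from before to after within an arm, together with some precision in the comparison of arms.

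**Working it through.** The plan gives no figure on this point to reproduce. The check traces the sequence and then sizes the consequence under stated assumptions.

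**Sequence**

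| | Clinic visit 1 (first biopsy) | Clinic visit 3 (second biopsy) |
|---|---|---|
| Meal | standard breakfast | standard breakfast |
| Capsules with the meal | fish oil or placebo, random order | placebo, everyone |
| Biopsy | end of visit, about 6 h | end of visit, about 6 h |

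**Inputs**
- From section 12: 20 per treatment group within each weight class, an anticipated 20% reduction, 80% power, 5% significance level.
- Assumed: order 1:1; an acute adipose effect that lowers a marker by a% of its mean, with a = 5, 10 or 20 for illustration; an SD of 22% of the mean. The protocol states no SD. This value is back-solved from 20 per group, a 20% difference and 80% power with a t-test; a normal approximation gives 22.6%.

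**Within-arm change.** With half the baselines lowered by a, the mean baseline falls by a/2 and every before/after change moves up by a/2. Taking a true chronic effect of -20 points in the n-3 arm and 0 in the placebo arm:

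| a | n-3 arm: -20 + a/2 | placebo arm: 0 + a/2 | difference |
|---|---|---|---|
| 0 | -20 | 0 | -20 |
| 5 | -17.5 | +2.5 | -20 |
| 10 | -15 | +5 | -20 |
| 20 | -10 | +10 | -20 |

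The difference between arms does not move, because order is random with respect to arm.

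**Precision of the between-arm contrast.** A shift of a in a random half of subjects adds variance a²/4. The SD becomes √(22² + a²/4) and the standard error at 20 v 20 is SD × √(2/20). Power is by normal approximation.

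| a | SD | SE | power |
|---|---|---|---|
| 0 | 22.00 | 6.96 | 0.820 |
| 5 | 22.14 | 7.00 | 0.815 |
| 10 | 22.56 | 7.13 | 0.800 |
| 20 | 24.17 | 7.64 | 0.744 |

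**Chance imbalance in order.** If the 12-week allocation is not balanced on order, let d be the difference between arms in the proportion given fish oil first. Its SD is √(0.25 × 2/n). The probabilities below are exact, from two independent Binomial(n, 0.5) counts.

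| n per arm | SD of d | P(\|d\| ≥ 0.20) | P(\|d\| ≥ 0.30) |
|---|---|---|---|
| 20 | 0.158 | 0.268 | 0.081 |
| 40 | 0.112 | 0.093 | 0.010 |

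In a given trial the between-arm contrast is displaced by a × d. At a = 10 and a typical d of 0.158 this is about 1.6 points, against an SE of about 7. At a = 20 with d = 0.20 or 0.30 it is 4 or 6 points. This is the same quantity as the extra variance above and should not be counted twice: at a = 20, √(6.96² + (20 × 0.158)²) = 7.64.

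**Which model term helps.** The shift exists only at baseline. A main effect of order in a repeated-measures model averages over both times and leaves the shift in the change. An order-by-time term captures it. In a model of the 12-week value adjusted for baseline, an order factor absorbs the offset in the covariate.

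**The case against.** The strongest reply is that the trial is randomised twice. Meal order is random, the 12-week allocation is random, and both Sample analysis and section 11 include a comparison between groups, so the a/2 shift falls equally on both arms in expectation and cancels. Chance imbalance in a randomised factor is ordinary sampling error, which the standard error already covers. All of this stands. A reader might infer that the n-3 versus placebo comparison is biased; the documents do not support that.

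The size also rests on an assumed input. Nothing in the protocol shows that one dose changes subcutaneous fat within about 6 hours. Taking a = 20 supposes that one dose does as much as section 12 expects of 12 weeks, and that 20% refers to inflammatory mediators such as interleukin-6, not adipose markers. At a = 5 or 10 the power loss is negligible. Question 4 is not split by weight class, so 40 v 40 is a fair denominator for it, and imbalance is rarer there. These points stand too.

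Two further readings are tempting and fail. One is that the protocol contradicts itself on when the first biopsy is taken. Study entry in the General approach is a loose label, and the participation schedule and visit table consistently place the biopsy at clinic visit 1. The other is that the randomisation is known to ignore meal order, or that the analysis is known to omit it. The protocol is silent on both, and such detail may sit in an analysis plan that was not available here.

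The reply does not remove the mismatch in capsule exposure between the two biopsies. The protocol fixes that mismatch, and both the before-and-after wording of objective 3 and the comparison across time in Sample analysis bring it into use.

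**Conclusion.** The point holds in a limited form. The sequence is certain from the text: the first biopsy follows fish oil or placebo capsules in random order, and the second follows placebo capsules in everyone. With 1:1 order, about half of the baselines (about 25 of the 50 subjects recruited per weight class) follow an acute n-3 dose. A within-arm before/after change would then be displaced by a/2, or 2.5 to 10 points over the illustrative range of a, and the placebo arm could show a rise that no chronic process caused. The comparison of arms keeps its expected value and loses some precision, appreciably only at the top of the range (power 0.82 to 0.74 at an SD of 22%). Whether a differs from zero is unknown. The case for acting is that the remedy is nearly free and order is a factor the trial already randomises.

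**What to change.** 1. State that question 4 is answered by the between-arm contrast in adipose markers, and that within-arm before/after changes are descriptive.
2. Include meal-capsule order in the adipose analysis, as order by time in the repeated-measures ANOVA or as a factor in a model of the 12-week value adjusted for baseline. An order main effect alone in the repeated-measures model is not enough.
3. Where the randomisation list still allows, balance the 12-week allocation on BMI group and meal order (2 × 2 = four strata).
4. Describe the first biopsy in section 8 and in the General approach consistently with the participation schedule, so that a reader knows it follows the meal and capsules.

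Cost: one or two model terms, four strata in the list and a few words of text. No visit or biopsy is added. Adjustment will not turn an exposed baseline into an unexposed one, but it stops the exposure from being read as change over time.
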